## 6.0 STATISTICAL CONSIDERATIONS

**Power for primary outcome.** Our primary outcome that we are using to power the study is reduction in pain interference. Based on PROMIS validation studies with chronic pain samples, a difference of 3 points or more between study arms was considered to indicate a clinically meaningful difference. The PROMIS website also gives the mean and standard deviation of the T-score metric ( $M = 50$ ,  $SD = 10$ ). We powered the analysis to be able to detect a 3-point difference (an effect size of  $d = .30$ ) between control and ET-LT, and then the same magnitude of effect between ET-LT and ET-SS (an effect size of  $d = .60$  for control versus ET-SS). Across 10,000 LMEM simulations, a post-attrition- $N = 255$ , we would have power  $>80\%$  to detect the study arm X time interaction.

**Missingness.** Data are likely to be missing not-at-random. This may lead to biased parameter estimates. Pattern-mixture modeling will test the sensitivity of our intervention analysis to missing data assumptions, by conducting sensitivity analyses after imputing missing data with a range of clinically plausible values using assumptions for missing data (e.g. best or worst case, with and without multiple imputation). With regard to survey data, in the previous ET trial, 353 of 390 participants (90.51%) completed the 6-month survey and 310 of 390 (79.49%) completed the 12-month survey. In completed surveys, data were missing on about 2% of core items. We expect similar rates in this study, that is, about 87% survey completion at 8 months. Thus, we increased the total sample size after attrition to 291 to increase the likelihood of detecting effects on the outcomes with 2 moderators: sex and number of chronic conditions.

**Quantitative analysis plan.** Intention-to-treat will be the data primary analyses.

**Assumptions and randomization effect.** We will report descriptive statistics for all demographic and clinical variables in both arms to ensure that randomization produced comparable groups; if not, variables with significant differences will be included as covariates in a sensitivity analysis. Sensitivity analyses (with and without covariate adjustment) will determine the robustness of covariate-related error control. All outcome variables will be examined using standard summary statistics, visualizations, and tests for normality and

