homoscedasticity. Data will be transformed for continuous outcomes that do not meet the assumptions of a normally distributed outcome. We will test for a main effect of clinic site. If significant, we will add clinic site to our models to control for its variance.

*Effectiveness of control vs. ET-LT vs. ET-SS.* Linear mixed effects models (LMM)—which account for dependence among successive observations for the same participant and can address incomplete data—will be used to examine effects of study arm (ET-SS vs. ET-LT vs. control, a between-subjects factor) on our outcomes over time. We will conduct specific treatment X time contrasts both between, and within, groups to test time-based effects. For binary, count, and other non-normal data, generalized mixed effects models will be used.

*Mediation and moderation effects.* Structural equation modeling (SEM) will explore the effects of mediation on the relation between study arms and our two primary outcomes. We anticipate that the impact of study arm on pain interference and psychological QOL will be mediated by SDT (competence, relatedness, and motivation), exercise, and pain catastrophizing at 4 months. SEMs involving ET use will be run separately for just the ET-SS and ET-LT arms. 2) We anticipate that sex, number of chronic conditions, and barriers to technology will moderate the indirect paths of the mediation models (see Figure 1, logic diagram).

*Impact of interim analyses on Type 1 error for whole sample analysis.* Findings that are significant in the interim but not the final analyses will be treated as non-significant. The final analysis will examine all data over time. For analyses that address the same hypothesis a Holm-Bonferroni correction will be applied.

**Qualitative analyses.** For each data set, a coding scheme of key themes will be constructed, based on the research questions (perceived benefits, barriers to use) and examination of the data. Each scheme will be pilot tested, then 2 trained coders will code an overlapping subsample of 20% of content. Once reliability is established (minimum Krippendorff's alpha of .80 per category), the coders will work independently in NVivo.

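### Section 6.0 does not fix how the baseline outcome and the randomisation strata enter the primary mixed model; one natural reading can cost precision in the 8-month contrasts

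*Combined protocol and SAP*

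**What the plan says.** Section 6.0 (effectiveness paragraph) describes a linear mixed model for study arm over time, and adds: "We will conduct specific treatment X time contrasts both between, and within, groups to test time-based effects". Outcomes are collected at months 0, 4 and 8 (Section 2.0, overview of methods). The paragraph names no baseline term, no common baseline mean and no strata.

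Covariates appear elsewhere:

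- Section 2.0, Specific Aim 2, lists baseline covariates, including baseline outcomes, without attaching them to a model. None of the three stratification factors is on that list.
- Section 6.0, on checking randomisation, says that "variables with significant differences will be included as covariates in a sensitivity analysis", and then: "Sensitivity analyses (with and without covariate adjustment) will determine the robustness of covariate-related error control". It does not say which version is primary.
- On clinic site, after a test of its main effect: "If significant, we will add clinic site to our models to control for its variance".

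Randomisation follows consent and baseline measurement and is stratified on gender, site (UW or community) and number of chronic conditions (Section 4.0, Patient Randomization). In Section 6.0, sex and number of conditions appear as moderators: the sample size was raised to "increase the likelihood of detecting effects on the outcomes with 2 moderators: sex and number of chronic conditions", and both are used again in the mediation models.

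The power paragraph sets 3 points "between control and ET-LT, and then the same magnitude of effect between ET-LT and ET-SS", and claims more than 80% power "to detect the study arm X time interaction" with 255 patients after attrition.

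**The concern.** Two statisticians could fit different primary models from this text. One would take month 0 as a response with its own mean in each arm. The other would adjust for the baseline outcome, as Aim 2 suggests. Because baseline is measured before randomisation, the arms share one expected baseline mean by design. A model that estimates three separate means gives up that information, and its contrasts of change from month 0 carry extra baseline noise. What is at stake is the precision of the two 3-point adjacent-arm contrasts, which are the comparisons that the hypotheses are about.

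The strata raise a smaller question. They were used to balance the arms but are not stated model terms, and whether site enters the primary model depends on a test on the trial data. It is also unclear whether clinic site means the two-level stratum or the six UW clinics listed under ET implementation and operation.

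**Working it through.** **Inputs from the plan.** Difference between adjacent arms 3 points; SD 10; 255 patients after attrition (Section 6.0). 291 randomised (Section 4.0). Completion "about 87% survey completion at 8 months".

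**Assumptions, because the plan gives no figure.** Equal allocation (291/3 = 97 per arm; 255/3 = 85). Month-4 completion 93%. Two-sided .05, before the Holm correction. Correlation rho between occasions .3, .5, .7 or .8, equal across pairs of occasions. SD 10 at months 4 and 8. Baseline SD 10, 9 or 8.

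**Step 1: the plan's own figure.** Arm by time interaction, noncentral F, 85 per arm, 8-month shifts of 0, 3 and 6 points, equal SDs:

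| Test form | rho .3 | .4 | .5 | .7 |
|---|---|---|---|---|
| 4 df, linear growth | 75.5% | 82.5% | 89.5% | 99.0% |
| 4 df, full effect by month 4 | 87.8% | 92.6% | 96.6% | 99.9% |
| 2 df, change to month 8 | 84.6% | 89.9% | 94.6% | 99.7% |

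More than 80% therefore reproduces in every form from rho of about .4. With 97 per arm and dropout modelled, the 4-df linear-growth test at rho .3 gives 78%.

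**Step 2: why the baseline mean matters.** For one patient, with baseline SD S0 and month-8 SD S8:

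- variance of change = S0² + S8² − 2·rho·S0·S8
- variance after baseline adjustment = S8²(1 − rho²)
- difference = (S0 − rho·S8)²

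The difference is a square, so the change contrast can never be the more precise one. It is zero when S0 = rho·S8.

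Example at rho .5 and S0 = S8 = 10: change 100 + 100 − 100 = 100; adjusted 100 × .75 = 75. With 85 per arm, the SEs are √(2 × 100/85) = 1.534 and √(2 × 75/85) = 1.328, and power for 3 points is 50% and 62%. With S0 = 8 the change variance is 64 + 100 − 80 = 84, against the same 75.

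**Step 3: the mixed model with dropout.** Generalised least squares information for 3 arms and 3 occasions, 97 per arm, completion 93% and 87%. Separate baseline means are compared with one common mean; power is Φ(3/SE − 1.96).

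| | rho .3 | .5 | .7 | .8 |
|---|---|---|---|---|
| SE, baseline SD 10 | 1.78 to 1.47 | 1.51 to 1.33 | 1.18 to 1.09 | 0.96 to 0.92 |
| Power, baseline SD 10 | 39 to 53% | 51 to 62% | 72 to 78% | 88 to 90% |
| Variance cut, baseline SD 10 | 32% | 23% | 13% | 9% |
| Variance cut, baseline SD 9 | 26% | 16% | 7% | 2% |
| Variance cut, baseline SD 8 | 19% | 10% | 2% | 0% |

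At baseline SD 9, power goes from 55 to 62% at rho .5 and from 76 to 78% at rho .7. At baseline SD 8 it goes from 58 to 62%, and stays at 78%. With baseline SD 10 and 79% completing month 8 (89% at month 4 assumed), the four pairs are 37 to 50, 48 to 58, 69 to 75 and 85 to 88%. First-order autoregressive correlation moves the power figures in the table by about one point.

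**Step 4: the strata.** Time-constant effects cancel in a contrast of changes. At rho .5, with strata explaining an assumed 10% of variance (291 patients, 94% and 87% completion), adding them moves the SE from 1.509 to 1.507 with separate baseline means, and from 1.328 to 1.304 with a common mean. After baseline adjustment, strata explaining 2 to 10% of variance add 0.1 to 2.5 power points over the four values of rho. In a 20,000-replicate simulation with the strata left out of the model, type I error of the change contrast was .048 to .050.

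**The case against.** The strongest reply is that the plan never specifies a separate baseline mean per arm. Aim 2 lists baseline outcomes as a covariate, and Section 6.0 foresees analyses with covariate adjustment. On that reading the loss is zero. This stands: what the documents show is an unreconciled model statement, and the loss of precision is conditional on how it is resolved.

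Second, the size depends on the baseline SD. Entry requires average pain of 3 to 10, which could narrow the spread of pain interference at baseline. The plan gives no baseline SD, so this cannot be settled, but it also stands: at baseline SD 8 most of the gain is gone from rho .7 upward.

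Third, leaving out the strata barely affects the planned contrasts. That stands as regards precision and type I error. What remains is prespecification.

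Three stronger readings are tempting:

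- A reader might infer that the plan ignores its baseline data. It need not: month 0 can serve as a response in the mixed model.
- A reader might infer that the stated power is wrong. That figure is for the overall interaction, not for a single adjacent-arm contrast, and it reproduces from rho of about .4.
- A reader might infer that clinic site must be the randomisation stratum. The text does not say so, and the six clinics are an equally possible meaning.

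**Conclusion.** The gap is real: Section 6.0 does not determine how baseline enters the primary model, and Aim 2 does not fill the gap. With separate baseline means, the 8-month adjacent-arm contrasts lose between nothing and a substantial amount of precision. Across the cases examined, a common baseline mean cuts the variance by 0% to 32%. At rho .5 this is worth 4 to 11 power points (58 to 62% at baseline SD 8, 51 to 62% at SD 10). If the Aim 2 covariate or a common baseline mean is used, nothing is lost.

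The range rests on assumed values for the correlation, baseline SD, allocation, month-4 completion and alpha. It is a matter of efficiency and prespecification, not validity: no bias or inflated type I error was found. The strata and site part carries little numerical weight. It matters because the primary model should reflect the stratified design and should not depend on a significance test.

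**What to change.** In Section 6.0:

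1. Specify one primary mixed model: either months 0, 4 and 8 with a baseline mean common to all arms, or months 4 and 8 with the baseline outcome as covariate.
2. Include gender, site (UW or community) and condition-count stratum as fixed effects in every case.
3. Delete the rule that adds site only if significant. Define clinic site (the randomisation stratum or the six clinics) and decide in advance whether any clinic term beyond the stratum is included.
4. Reconcile the Aim 2 covariate list with Section 6.0, and state which of the versions with and without covariates is primary.

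The cost is SAP wording and a few model degrees of freedom. No extra patients, visits or data are needed, because the baseline outcomes and strata are known before randomisation.

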- *Medical focus – whole-person focus.* All chronic diseases share certain features. Patients feel frustrated, discouraged, and lonely. They face continual, ongoing ups and downs. NIH funded us to develop one program that would address these common needs shared by all patients with MCCs. ET's focus is therefore the whole person, not the management of any particular disease. In our completed trial, ET improved QOL among those with high levels of primary care use across a wide range of conditions. Older adults in that RCT reported that ET increased happiness by being fun, not just utilitarian. In our pilot studies, all were enthusiastic about the smart system's potential, not only for health tasks (e.g. medication reminders) but also for music and social interaction. In a national survey of more than 1800 adult users, top requests included jokes, games, and music, underscoring the expectation of pleasure. We predict the smart system's ease of use will increase sustained use of ET's content, prompt more overall use and higher quality of life.
- *Groundbreaking.* This will be the first large RCT of a smart system that is likely to take the health field by storm. The knowledge gained could significantly improve future designs and implementations of smart devices.

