#### **Specific Aim 2: Conduct a randomized clinical trial to test the following hypotheses.**

Figure 1 describes the 3-arm RCT. Baseline covariates include race/ethnicity, education, baseline outcomes, life stresses, health service use, and technology use.

1. Primary outcomes: For those in ET-SS (vs. ET-LT vs. Control): pain interference will decrease and psychosocial quality of life will increase.

2. Secondary outcomes: ET-SS (vs. ET-LT vs. Control) will increase ET use at 8 months, increase physical quality of life, well-being, and communication with doctor. Pain intensity, 30-day hospital readmission rates, health distress, loneliness, and

[figure not shown]

Figure 1. Logic Diagram

irritability will decrease. We also plan to compare ET-LT to the UC control, given the unique focus of chronic pain in this study.

3. **Mediators:** Self-Determination Theory constructs of competence, social relatedness, and intrinsic motivation, together with exercise and pain catastrophizing, will mediate the effects of study arms on outcomes.

Additionally, use of ET at 4 months will mediate effects of study arms (ET-LT vs. ET-SS) on 8-month ET use.

4. **Moderators:** ET-SS (vs. ET-LT vs. Control) will show greater improvements for a) women (vs. men), b) patients with more (vs. fewer) chronic conditions, and c) patients with fewer barriers to using technology for the primary and secondary outcomes.

5. **Exploratory analyses:** We will measure level of use of each ET service, how it differs between the two ET arms, and perceptions of Elder Tree and the Clinician Report. We will also measure alcohol use, smoking, and falls.

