## 5.0 MEASURES AND DATA COLLECTION

Participants will be tracked for a total of 8 months. Data will be collected from: electronic health records (EHR), participant surveys (at months 0, 4, and 8 months), qualitative interviews, and ElderTree use data. Table 2 lists quantitative and qualitative measures, data sources, psychometrics, and references to validation studies.

**Quantitative.** Surveys conducted at months 0, 4, and 8 are expected to take 20-30 minutes and will assess psychosocial and physical QOL, pain, 30-day readmits, health distress, well-being, loneliness, communication with doctors, irritability, alcohol use, smoking, falls, and hypothesized mediators of competence, relatedness, motivation, exercise, and pain catastrophizing. Surveys will be mailed to patients with a self-addressed stamped envelope. Patients will be phoned if they do not respond after 2 weeks. Patients can contact study staff for more detail if questions arise. Contact with patients can be requested by staff if data integrity or compliance issues are detected in ongoing data review. Survey data will be entered into REDCap.

Table 2. Measures Used to Evaluate ET-SS vs. ET-LT vs. Control				
Endpoint	Measure	# Qs	Source	Psychometrics
Primary Outcomes				
Pain Interference	Promis-29 v2.1	4	Patient	$\alpha$ range = .88 - .97 
Psychosocial QOL	Promis-29 v2.1	12	Patient	N/A
Secondary Outcomes				
ET use @ 8 mos.	# logons	N/A	ET	N/A
Physical QOL	Promis-29 v2.1 & Late Life Function and Disability Instrument	53	Patient	N/A
Pain Intensity	Promis-29 v2.1 & Lorig	3	Patient	N/A
30 day readmits	Admissions	1	Patient	N/A
Health distress	Lorig Health Distress Scale	4	Patient	$\alpha = .87^{61}$
Well-being	WHO Well-Being Index	5	Patient	$\alpha = .93^{62}$
Loneliness	NIH Toolbox	5	Patient	$\alpha = .93^{63}$
Comm w/doctors	Lorig Comm w. Physicians	3	Patient	$\alpha = .89^{61}$
Irritability	Brief Irritability Test (BITe)	5	Patient	$\alpha > .88^{64}$
Mediator Candidates				
ET use @ 4 mos.	# page views w/o nav.	N/A	ET	N/A
Competence	Disease Self-Efficacy	6	Patient	$\alpha = .91^{65}$
Relatedness	Bonding	5	Patient	$\alpha = .85^{66}$
Motivation	Tx Self-Regulation subset	4	Patient	N/A
Exercise	Scale created for study	4	Patient	N/A
Pain Catastroph.	Pain Catastrophizing Scale	13	Patient	$\alpha = .87$
Moderator Candidates				
Sex	Baseline survey	1	Patient	N/A
Chronic conditions	Total #	N/A	EHR	N/A
Barriers to tech	Created for study	2	Patient	N/A

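### The mediation plan names month-4 mediators but does not say that their month-0 values, which are collected, enter the model; where an arm shifts a mediator, stable patient differences can then appear as mediation.

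*Combined protocol and SAP*

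**What the plan says.** Section 6.0, under mediation and moderation, sets the scope: "Structural equation modeling (SEM) will explore the effects of mediation on the relation between study arms and our two primary outcomes". It then says that the arm effects on these outcomes "will be mediated by SDT (competence, relatedness, and motivation), exercise, and pain catastrophizing at 4 months". No covariates are named for these models, and the month of the outcome is not given.

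Specific Aim 2 introduces the trial's logic diagram with this list: "Baseline covariates include race/ethnicity, education, baseline outcomes, life stresses, health service use, and technology use". Baseline mediators are not on it.

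Section 5.0 shows that the values will exist. "Surveys conducted at months 0, 4, and 8 are expected to take 20-30 minutes", and their content includes the "hypothesized mediators of competence, relatedness, motivation, exercise, and pain catastrophizing".

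For ET use as a mediator, the one written hypothesis (Specific Aim 2, item 3) is that "use of ET at 4 months will mediate effects of study arms (ET-LT vs. ET-SS) on 8-month ET use". Section 6.0 adds that models involving ET use are fitted in the two ET arms only, without naming their outcome. Table 2 lists 4-month ET use as a mediator candidate without tying it to any one outcome.

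**The concern.** A mediated effect is the product of two paths, arm to mediator (a) and mediator to outcome (b). Randomisation makes the first a fair comparison. It does nothing for the second, because nobody is randomised to a level of catastrophizing or self-efficacy. Patients who always catastrophize more also tend to report more pain interference, so month-4 catastrophizing predicts month-8 interference even if changing it would change nothing. If the arm also shifts catastrophizing, the product of a real first path and a spurious second path is read as a mechanism. The month-0 mediator is the natural partial remedy, since it carries much of the same stable difference.

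At stake is what the trial reports about how ET works, not whether it works.

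The ET-use models raise a smaller question of wording. The background expects the smart system's ease of use to "prompt more overall use and higher quality of life", yet the written use hypothesis ends at later use. Nothing states outright that use will be tested as a route to the primary outcomes.

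**Working it through.** **Plan's own figure.** The documents give no power, sample size or effect size for mediation, so there is nothing to reproduce. The sample size is borrowed from the power paragraph: 255 after attrition, or 255 / 3 = 85 per arm if allocation is equal (an assumption).

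**Inputs not in the documents, all assumed.** Test-retest correlation r = 0.6-0.7 for mediator and outcome; correlation c = 0.4-0.6 between their stable parts (traits); arm effect on the mediator 0.4 SD (ET-SS vs Control); true mediator-to-outcome effect zero. Variables have SD 1. Mediator and outcome are linked only through their traits. Ordinary regression paths stand in for the SEM.

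**Step 1: the spurious b path.** Within arm, month-4 mediator and month-8 outcome correlate at rc. The expected coefficient of the month-4 mediator is then:

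- with the month-0 outcome only: rc(1 - r) / (1 - r²c²)
- with the month-0 outcome and month-0 mediator: rc(1 - r) / (1 + r - 2r²c²)

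| r, c | rc | Month-0 outcome only | Plus month-0 mediator |
|---|---|---|---|
| 0.6, 0.4 | 0.24 | 0.096 / 0.9424 = 0.102 | 0.096 / 1.4848 = 0.065 |
| 0.6, 0.6 | 0.36 | 0.144 / 0.8704 = 0.165 | 0.144 / 1.3408 = 0.107 |
| 0.7, 0.4 | 0.28 | 0.084 / 0.9216 = 0.091 | 0.084 / 1.5432 = 0.054 |
| 0.7, 0.6 | 0.42 | 0.126 / 0.8236 = 0.153 | 0.126 / 1.3472 = 0.094 |

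The true value is zero in every cell. The month-0 mediator removes 35-40% of the bias that the baseline outcome leaves (for example, 1 - 0.065 / 0.102 = 36%). It does not remove all of it, because one measurement captures the trait with error.

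**Step 2: the spurious indirect effect.** Multiply by the arm effect of 0.4. The range is 0.4 × 0.091 = 0.036 to 0.4 × 0.165 = 0.066 outcome SD with the baseline outcome only, and 0.4 × 0.054 = 0.022 to 0.4 × 0.107 = 0.043 with the month-0 mediator added. If the arm effect on the mediator is zero, the product averages zero whatever the b path.

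**Step 3: how often it is declared.** Simulated trials with N = 255, counting mediation when both paths are significant at two-sided 0.05:

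| Arm effect on mediator | Month-0 outcome only | Plus month-0 mediator |
|---|---|---|
| 0 | at or below 5% | at or below 5% |
| 0.4 SD | about 37-73% | about 13-36% |

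A separate set of runs with c = 0.5-0.7 gives the same ordering: 38-55% against 19-39% at 0.3 SD, and 70-96% against 30-58% at 0.6 SD. Part of the fall in these rates comes from a larger standard error for the b path once the correlated month-0 mediator is in; Step 1 shows the change in bias itself.

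**Step 4: does the extra term cost power?** It does not in these runs. With a true b path of 0.2 and an arm effect of 0.3 SD (c = 0.5-0.7), mediation is detected in 54-58% of trials with the baseline outcome only and 66-80% with the month-0 mediator added. The reason is a more precise a path: its standard error is sqrt(2/85) × sqrt(1 - r²), which is 0.153 × 0.80 = 0.12 at r = 0.6 and 0.153 × 0.71 = 0.11 at r = 0.7, against about 0.14-0.15 without the term.

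**Step 5: ET use.** There is no month-0 value of ET use. With 85 per arm, a 0.3 SD arm effect on use, trait correlation 0.4-0.6 and adjustment for the month-0 outcome only, false mediation is roughly 18-40%. A use model on the primary outcomes therefore carries the same risk, without this remedy.

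**The case against.** **Silence is not exclusion.** A reader might infer that the plan fits the models without month-0 mediators. The documents do not say so: section 6.0 gives no covariate set, the Specific Aim 2 list is worded as what the covariates include, and the logic diagram is not shown in the copy reviewed. This stands; the defect is an omission in the text.

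**Worst case.** Models with no baseline terms at all would give 73-75% false mediation at 0.4 SD. That should not be attributed to the plan, because baseline outcomes are on its covariate list. The fair comparison is the one in Step 3.

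**It needs an arm effect on the mediator.** A reader might infer that stable differences will always pass for mediation. They will not, as the zero row of Step 3 shows. The plan does, however, hypothesise mediated arm effects, so the condition is one it expects to meet.

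**Multiplicity.** Holm-Bonferroni applies to analyses of the same hypothesis. If it spans the five mediators, the strictest step (0.01) gives 14-44% with the baseline outcome only. That is lower, but still well above the nominal level.

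**Existing safeguards.** Section 6.0 promises that "Sensitivity analyses (with and without covariate adjustment) will determine the robustness of covariate-related error control", and it adds covariates on which the arms differ significantly. Neither is tied to the mediation models or to month-0 mediators, and an imbalance rule misses the problem, which exists when arms are perfectly balanced. The verb explore in section 6.0 helps, but Specific Aim 2 lists mediators among the hypotheses to be tested, apart from its exploratory item.

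**ET use.** A reader might infer that ET use is planned as a mediator of later use only. Section 6.0 limits the modelling to the two primary outcomes before it mentions ET-use models, and Table 2 sets no such limit. ET use is understandably absent from the three-arm mediator list, because Control has no ET. What remains is that the outcomes of those models are not written down.

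**Conclusion.** The point holds as an omission that can be repaired at almost no cost. The plan names month-4 mediators, lists baseline outcomes but not baseline mediators, and collects all five mediators at month 0. Where an arm shifts a mediator by 0.4 SD and the true mediator effect is zero, false mediation is about 37-73% with the baseline outcome only and about 13-36% with the month-0 mediator added.

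These rates rest on the assumed test-retest and trait correlations, the assumed arm effect, equal arms of 85, and testing at 0.05 without Holm correction. The direction and ordering held in every setting tried with an arm effect on the mediator; the exact percentages should not be read as predictions for this trial.

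Two limits apply. The remedy reduces the confounding and does not remove it. And the arm comparisons on pain interference and psychosocial QOL use mixed models that do not involve the mediators, so the trial's main result is unaffected. The ET-use part is a clarification of wording. This is a change that should be made, not one on which the trial's validity depends.

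**What to change.** 1. In section 6.0 (mediation and moderation effects), state that the month-0 value of each survey mediator and the month-0 outcome enter both equations of each mediation model.
2. Label all indirect effects as exploratory, in section 6.0 and in Specific Aim 2, item 3.
3. Add a sensitivity analysis for unmeasured mediator-outcome confounding, for example how strong a residual correlation between the two equations would have to be to reduce the indirect effect to zero.
4. In Specific Aim 2, item 3, and in section 6.0, state that the ET-SS vs ET-LT use models have 8-month pain interference and psychosocial QOL as outcomes, adjusted for their month-0 values and the baseline covariates already listed. Note there that ET use has no month-0 value, so these results carry the same caveat on confounding with less protection.

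The cost is a few sentences of plan text, some extra model terms and one sensitivity analysis. No new data are needed, because the month-0 surveys already contain every value required.
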